Bachelor's and master's students need to seek ethical approval through the principal researcher.

II General Information

1. What is the name of the study

Leidt het focussen op de functionaliteit van het lichaam tot meer lichaamstevredenheid bij vrouwen die bariatrische chirurgie hebben ondergaan?

[Does focusing on body functionality improve body image among women who have undergone bariatric surgery?

2. What is the name of the study used for the participants (if applicable)

Positief Lichaamsbeeld

[Positive Body Image]

3. In general terms, what is the subject of the study?

This study investigates improving body image among women who have undergone bariatric surgery approximately 6 months ago, by having them focus on their *body functionality* (i.e., everything the body can *do*).

4. It concerns a:

- $\hfill\square$ Line of research
- X Study project
- 5. In case of students: NA

6. Are any grant providers involved in the study?

No

7. What is the name of the PRINCIPAL researcher?

[name] and [name]

8. What is the email address of the PRINCIPAL researcher?

[contact] and [contact]

9. Which faculty initiated this study?

Faculty of Psychology and Neuroscience

10. Which department or section instigated the study?

Department of Clinical Psychological Science

11. At which organisation will the study be carried out?

Nederlands Obesitas Kliniek (NOK)

12. Are there any protocols related to and approved by the ERCPN (formerly named ECP – Ethical Committee Psychology) regarding the procedures, interventions and measurements described in this application? If so, then please provide the reference number(s) of these protocols so that the committee can take this into account (for your benefit).

No

III Description of the Study (please keep to 500 words maximum)

1. What is the background of the study?

In this research we make a distinction between two perspectives toward the body: how the body looks, and what the body can do. Often the focus lays on the appearance-related aspects of the body, and there is less focus on what the body can do and how it enables us to do the things that we enjoy and find important in life. This last perspective focuses on body functionality, and refers to everything the body is able to do, in contrast to how the body looks. Body functionality comprises physical capacities and movement (e.g., strength, stamina, walking, biking). It also comprises aspects such as health (e.g., healing from a cold), creativity (e.g., drawing), social contact and communication (e.g., body language), and bodily senses (e.g., smell). In prior experimental research, women with a negative body image were instructed to focus on their body functionality with the help of three structured writing exercises. This led to an improvement in body satisfaction and body appreciation.

Based on these positive results, the Nederlandse Obesitas Kliniek (NOK; Dutch Obesity Clinic) decided to offer this intervention to women with obesity who have undergone a bariatric surgery approximately 6 months ago. After bariatric surgery, the NOK offers standard aftercare involving psychological support to help clients adjust in the period after surgery, and to achieve and

maintain a healthy weight. The NOK has asked us to deliver and evaluate the present intervention among their clients who have undergone bariatric surgery.

We would like to evaluate whether focusing on body functionality has a positive impact on the body image of women who have undergone bariatric surgery. Improving body image is important because a negative body image is related to (further) weight gain, physical inactivity, unhealthy eating behaviour, negative mood, and low self-esteem. Recent research has also shown that positive body image is the most important predictor of weight loss and maintenance.

2. What are the hypothesis and study question (in layman's terms)?

Research questions: Does focusing on body functionality lead to (1) a more *positive body image* and (2) a more *positive self-image* among women who have undergone bariatric surgery approximately 6 months ago?

Hypotheses: In comparison to NOK clients in the waitlist comparison group, NOK clients in the experimental group will experience improvements in (1) *positive body image* and (2) *positive self-image*, at posttest, follow-up 1, and follow-up 2.

3. What measurements and outcome measures (depended variables) are used?

- Body Appreciation Scale
- Physical Condition Subscale
- Body Areas Satisfaction Subscale
- Self-Objectification Questionnaire
- Body Responsiveness Scale
- Rosenberg Self-Esteem Scale
- Self-Kindness Subscale

NOK clients will also complete questions assessing their self-reported age, sex, height, and weight.

4. What is the statistical approach?

Statistical design:

- What are the independent and dependent variables?
- Is it a correlational or (quasi-)experimental design?
- Are human subjects randomly assigned to the conditions?
- For each independent variable, what design is used: within-groups or between-groups?

The study will take place entirely online, and comprises three writing exercises and four measurement points, spread over a period of 95 days.

• Day 1: Informed consent + Pretest (15 minutes) + Writing Exercise 1 (15 minutes)

- Day 3: Writing Exercise 2 (15 minutes)
- Day 5: Writing Exercise 3 (15 minutes) + Posttest (15 minutes)
- Day 12: Follow-up 1 (15 minutes)
- Day 95: Follow-up 2 (15 minutes)

We aim to test 100 female clients from the NOK: 50 clients will be randomised to the experimental group (intervention) and 50 clients will be randomised to the waitlist comparison group.

Clients in the experimental group will complete all aspects of the study, described above. Clients in the comparison group will only complete the assessments at pretest, posttest, and follow-ups. At the end of Follow-up 2, they can decide to receive the writing exercises.

5. How many subjects are measured based on a statistical power analysis?

We will need 82 clients. This is based on a power analysis with a (f = 0.25), $\alpha = 0.05$, and an 80% likelihood of detecting a true effect. We aim to test 100 clients to compensate for potential dropout.

6. Why should this study be done?

Improving body image is important because a negative body image is related to (further) weight gain, physical inactivity, unhealthy eating behaviour, negative mood, and low self-esteem. Positive body image is the most important predictor of weight loss and maintenance.

7. Is there any additional relevant information?

The NOK declares that they would like to use this intervention with their clients, and has asked us to evaluate its effectiveness. The participants are clients who have undergone bariatric surgery approximately 6 months ago at the NOK. The NOK plans to use the present intervention to foster the (further) psychological well-being of its clients.

As described (page 3), we have already tested this intervention among a group of women with a negative body image. We will be using the same intervention material for the present research (see ethics application with approval number: ECP-137 13_02_2014).

The clients will complete the informed consent sheet online, at the beginning of the first session (Day 1, page 4).

8. What documents are enclosed in the application?

- □ Advertisement
- X Statement of consent of the external organisation where the study takes place
- X Information letter for subjects
- X Statement of consent form for subjects
- □ Cover story for subjects
- X Debriefing form for subjects

 Other documents, namely:.....

9. Only for adult subjects:

Participants are asked to be added to the test subject database (FPN-wide database with subjects who have previously indicated their willingness to participate in scientific research).

No

This concerns a database for and by FPN researchers, which is managed by the Research Support Department (RSD) of the FPN and contains details of subjects over the age of 18 years who are willing to participate in scientific research. The persons involved have expressly

given their consent. For more information visit:

www.maastrichtuniversity.nl/fpn/proefpersonen

IV Ethically Sensitive Aspects of the Study

Please explain below the method of dealing with ethically sensitive aspects of the planned study:

- 1. Please mark the relevant age and categories (multiple entries possible):
 - □ Students
 - X >17 years, with legal and mental capacity
 - <12 years</pre>
 - X Patients
 - □ 12-17 years, with legal and mental capacity
 - □ 12-17 years, without legal and mental capacity
 - □ >17 years with legal and mental capacity with cover story

2. How will informed consent be obtained and recorded? Please mark the relevant form(s)

Form 1

Forms
Form 1: For studies with persons of age and with legal and mental capacity, consent must be given by the person involved.

- Form 2: For studies with persons under the age of 12 years, consent must be given by at least one parent or guardian.
 - Form 3: For studies with persons under the age of 18 years but over 11 years of age with legal and mental capacity, consent must be given by the child in addition to at least one parent or guardian.
- Form 3: For studies with persons (including children over 11 years of age) lacking legal and/or mental capacity, consent must be given by at least one parent or guardian or other (legal) representative.

Note: In case the absence of legal and/or mental capacity is temporary, renewed informed consent should be obtained from the subject directly once the capacity/capacities has/ve been re-established.

• Form 4: For studies with persons of age and with legal and mental capacity involving a cover story, consent must be given by the person involved.

3. What are the inclusion criteria?

Inclusion criteria: De NOK clients who are (1) women between 18 and 65 years old, (2) have undergone bariatric surgery approximately 6 months prior, and (3) qualify for NOK standard aftercare.

4. What are the specific exclusion criteria?

NA

5. Please describe in plain language what actions are required of the subjects or what behaviour will be observed:

Clients of the NOK (who meet the inclusion criteria) will receive information about the study from their treatment provider at the NOK, and can apply for the study via email. Clients can decide whether they would like to send us an email or not. If the client sends us an email, they will receive extended information about the study. Afterward they can decide themselves whether they would like to take part in the study or not. This decision has no consequences for the clients' further treatment at the NOK. If the client would like to take part in the study, she will be randomised to the intervention or comparison group. Afterward, the client will follow the research procedure (page 4). Clients may withdraw from the study at any moment, without needing to provide a reason. This also has no consequence for their treatment at the NOK.

- 6. What is the maximum load per subject per experiment? Please provide the following:
 - Maximum number of hours per session = 0.5
 - Maximum number of sessions per day = 1
 - Maximum number of days per experiment = 5
 - Total number of hours per participant per experiment = 1 hour and 45 minutes

7. Does the study include the use of equipment and measuring instruments?

No

8. Are there any risks of damage and discomfort involved for the participants of the study?

No

9. Does the study involve video and audio recordings of subjects?

No

10. Are the subjects provided with all the information about the study beforehand?

Yes

11. Does the study involve deception?

Deception is when participants are not informed beforehand of the true nature of the study and what is expected of them. For research purposes, deception is vital to avoid socially desirable answers and demand characteristics, but it also goes against the principle of active, informed consent. In other words, it is a serious measure that should only be used if sufficiently motivated and surrounded with appropriate safeguards, including adequate debriefing after participation. Deception is not allowed in studies involving minors (< 18 years).

No

12. How much time are the subjects given to decide on participation?

Clients from the NOK who have undergone bariatric surgery approximately 6 months ago may take part in the study. Because we would like to keep this relatively consistent, clients will have approximately 2 weeks to decide whether they would like to take part or not.

13. What is the reward per participant per experiment:

Compensation per subject cannot be too great, as that would interfere with reasonable consideration and as such voluntary participation.

The FPN generally awards a maximum of EUR 7.50 per hour in cash or gift vouchers or (for students) 1 research participation credit with the possibility of a raffle for a predetermined gift amount at the end of the study among subjects who participated for the entire duration of the study. In case of a raffle, the content of the prize and chances of winning should be announced in advance.

In case of early termination of participation in the study, the participant will still receive the promised amount of compensation. If multiple compensations are used for repeated measurements, these will be awarded in proportion to the number of participations. Participation credits are registered via the Research Participation System (also called SONA) https://maastricht-fpn.sona-systems.com. Researchers (and students) need to comply with the rules and regulations of SONA.

X Compensation (maximum of EUR 7.50 per hour); for higher rates, please explain why:

Every client will receive 15 Euro (VVV gift voucher).

14. Are the subjects debriefed after their participation in the study?

- □ Yes, both in oral and written form (please provide written form with this application)
- X No, please explain: Clients will receive a debriefing letter via email. They will also receive our

contact information (email and telephone number) should they have any questions.

In case of deception, there is always a debriefing (in oral and written form) immediately after having participated in the study. A debriefing is also required if the purpose of the study has not been explained beforehand or if the provided information was incomplete. The explanation should be given in plain language, with emphasis on the actions of the participants and/or what was asked of them and why.

15. Does the subject participate in other related experiments alongside this one?

No

16. Please indicate in which way the personal and study data are stored.

- X All data is stored confidentially
- □ All data is stored confidentially and encrypted
- □ All data is stored anonymously

The subjects' privacy should be respected and protected at all times. Personal data (all data that can be traced back to individuals directly or indirectly) should be stored in encrypted form separately from obtained study data and be treated confidentially by researchers. This personal data may not be kept longer than necessary to the ongoing study. An exception is when subjects have given their approval to retain their personal data longer for a clearly defined purpose, such as follow-up studies. Raw study data (completed questionnaires and other scoring lists) must be kept for at least 10 years after publication.

The difference between confidential and anonymous data storage; storage of personal data:

- Anonymous storage means that study data can in no way be traced back to the subject. That means there are no links (through numbers or other forms of encryption) to the personal data of subjects and the data cannot be used to identify the subject that it relates to. Anonymous storage is preferable to confidential storage.
- **Confidential** storage includes traceability. That means that study data can be traced back to the subject.

17. Do the subjects receive feedback regarding the provided data on an individual basis?

No

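### Does measuring the posttest straight after Writing Exercise 3, in the intervention arm only, let a momentary response pass as improved body image?

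*Protocol*

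**What the plan says.** Protocol III.4 lists the sessions. The third exercise and the first outcome assessment share a day: "Day 5: Writing Exercise 3 (15 minutes) + Posttest (15 minutes". Two assessments without an exercise follow: "Day 12: Follow-up 1 (15 minutes" and "Day 95: Follow-up 2 (15 minutes". For the other arm it says: "Clients in the comparison group will only complete the assessments at pretest, posttest, and follow-ups". Waitlist clients may take up the intervention only once outcome measurement is over: "At the end of Follow-up 2, they can decide to receive the writing exercises".

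Protocol IV.6 limits the load: "Maximum number of sessions per day = 1" and "Maximum number of hours per session = 0.5".

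Protocol III.2 predicts improvement in positive body image and positive self-image, relative to the waitlist group, "at posttest, follow-up 1, and follow-up 2".

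Protocol III.5 gives the sample size: 82 clients for f = 0.25, alpha 0.05 and 80% power, raised to 100 for dropout.

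**The concern.** The two arms reach the posttest in different circumstances. Intervention clients have just spent a quarter of an hour writing about what their body can do; waitlist clients have done nothing comparable. A difference at that moment is a real effect of assignment, but it may be a passing response to the task rather than a change in how clients see themselves.

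The rationale in III.1 and III.6 is about consequences that take time, such as weight, activity, mood and self-esteem, and III.7 says the clinic wants to use the intervention. If a posttest difference alone could carry the conclusion, an effect gone a week later might be reported as improved body image. The protocol states no explicit rule for a result that appears at posttest and not later.

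**Working it through.** **1. Is the asymmetry real?** Yes. Exercise 3 and the posttest take 15 + 15 = 30 minutes, which is exactly the half-hour limit for the one session allowed per day. The total in IV.6 agrees: Day 1 (30) + Day 3 (15) + Day 5 (30) + Day 12 (15) + Day 95 (15) = 105 minutes, the stated 1 hour 45 minutes. The comparison arm does assessments only.

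**2. Do the follow-ups share it?** No. Neither follow-up has an exercise attached. They fall 12 − 5 = 7 and 95 − 5 = 90 days after the last exercise. Because the waitlist is offered the exercises only after follow-up 2, both remain controlled comparisons. The data that separate a passing response from a lasting one are therefore collected.

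**3. Does the hypothesis rest on the posttest?** No. It joins the three time points with *and*. Read plainly, a difference at posttest only does not confirm it.

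**4. Does the sample size rest on the posttest?** Inputs from III.4 and III.5: f = 0.25, alpha 0.05, two groups, four measurements (m = 4). The correlation between measurements, rho, is not stated; 0.5 is assumed. For a between-groups F test over repeated measurements:

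- λ = N·f²·m / (1 + (m − 1)·rho)
- N = 82: λ = 82 × 0.0625 × 4 / 2.5 = 8.2; power with F(1, 80) = 0.808
- N = 80: λ = 8.0; power = 0.798

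So 82 is the smallest even total reaching 80%, and the stated figure is reproduced. A single time point would need 128 (F test) or 126 (normal approximation, d = 2f = 0.5). The 82 thus fits a test over all four measurements, not the posttest alone.

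**5. What if the effect were only momentary?** The protocol gives no size for such a response. As an illustration, take the whole 0.5 SD at posttest and zero afterwards, one scale, 41 per arm, two-sided 0.05, rho = 0.5.

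- Posttest contrast alone: noncentrality 0.5 × √(41/2) = 2.26; power 0.61. Adjusted for pretest, d = 0.5/√0.75 = 0.577; power 0.73.
- Mean of four measurements: shift 0.5/4 = 0.125 SD; SD of the mean √(2.5/4) = 0.79; standardised difference 0.158; power 0.11 (0.13 to 0.10 for rho 0.3 to 0.7).
- Significant at all three time points, as the hypothesis reads literally: below 0.01 (simulation).

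The 61% to 73% arises only if the posttest is read by itself, which no section proposes.

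**The case for a change.** The strongest reply is that the word *and* in the hypothesis cannot be the working success criterion, because the trial is not sized for it. With a 0.5 SD effect present at all three later time points, 41 per arm and no pretest adjustment, significance at all three has power of only about 0.36 (0.30 to 0.42 for rho 0.3 to 0.7), far below 80%. The hypothesis and the power statement therefore do not together fix one decision rule, and a mixed pattern is left open.

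That observation is correct, but it does not make the protocol wrong. III.2 is a prediction, requested in lay terms on a form that limits the study description to 500 words. Turning it into a decision rule over time points is ordinary content of a statistical analysis plan, which may exist and is not shown. Neither reading, the test over four measurements or the requirement at every time point, lets the posttest carry the claim alone.

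One could ask for an explicit rule, such as a posttest difference plus one at either follow-up. That is a trade-off rather than a correction:

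- It is looser than the hypothesis as written.
- It keeps the ambiguous time point as a compulsory hurdle, so an effect clear at Day 12 and Day 95 but missed on Day 5 would not count.
- If significance is required at the follow-up, it holds momentary-only effects to about 4%, but lowers power for a persistent effect from 0.61 to 0.54 (unadjusted, rho 0.5).
- If only the same direction is required, about 49% of trials with a momentary-only effect still pass (47% to 50% for rho 0.3 to 0.7), against 61% for the posttest alone.

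**Conclusion.** The concern does not hold. The Day 5 asymmetry is real, and a posttest difference should be understood as an immediate effect. But measuring straight after the last exercise and again 7 and 90 days later, against a control group that is still untreated, is how an immediate effect is told from a lasting one. The hypothesis names all three time points, and no section reads the posttest alone. The stated 82 is reproduced by a test over four measurements.

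Under that test a posttest-only effect of 0.5 SD would be positive in about 11% of trials. This rests on an assumed correlation of 0.5, 82 completers, one scale and an assumed size for the momentary response. That the four-measurement test is the intended one is inferred from the sample size, not stated. What is left open, the reading of a mixed pattern, is detail for the statistical analysis plan and not an error or contradiction in this protocol.

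### In the intervention arm only, the Day 5 posttest shares a single session with Writing Exercise 3, so posttest data may be lost selectively in that arm

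*Protocol*

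**What the plan says.** The schedule in Protocol III.4 reads "Day 5: Writing Exercise 3 (15 minutes) + Posttest (15 minutes" minutes for Day 5. The load limits in IV.6 are "Maximum number of hours per session = 0.5" and "Maximum number of sessions per day = 1".

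The arms differ in what they do. For the intervention arm, III.4 says "Clients in the experimental group will complete all aspects of the study, described above". For the waitlist arm it says "Clients in the comparison group will only complete the assessments at pretest, posttest, and follow-ups".

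The hypotheses in III.2 name the posttest as one of three time points at which the arms are compared; the other two are the follow-ups. These are scheduled without an exercise, for example "Day 12: Follow-up 1 (15 minutes" minutes.

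On leaving, IV.5 says "Clients may withdraw from the study at any moment, without needing to provide a reason". On dropout, III.5 says "We aim to test 100 clients to compensate for potential dropout", against a stated requirement of 82.

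**The concern.** Randomisation makes the arms comparable at entry. They stay comparable at posttest only if the chance of supplying a posttest does not depend on arm in a way tied to the outcome. Here an intervention client meets the questionnaire as the second half of a sitting that opens with a writing task. A woman who does not feel like writing that day, or stops halfway, may never reach the questionnaire. No comparison client faces that step.

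Women who give up on the exercise could plausibly be those who gain least from it, although the protocol gives no evidence either way. If so, the remaining intervention clients would look better than the full arm, and the posttest difference would be too large. Over-enrolment replaces numbers but not the women lost. Adjusting for the pretest removes only the part of the loss that the pretest explains.

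This belongs in the protocol and not only in an analysis plan. How a questionnaire is delivered is decided before data collection, and a posttest missed on Day 5 cannot be collected afterwards.

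**Working it through.** **1. The plan's own sample size.** Inputs from III.5: f = 0.25, α = 0.05, power 80%, 82 clients. For a repeated-measures ANOVA, between-groups factor, with 2 groups and m = 4 measurements, λ = N f² m / (1 + (m − 1)ρ) with 1 and N − 2 degrees of freedom. With ρ = 0.5 (assumed; the protocol gives no correlation), the smallest even N is 82, with power 80.8%. The figure reproduces and is not in dispute. The implied allowance for loss is 1 − 82/100 = 18%, with no split by arm.

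**2. Is Day 5 one session?** Exercise 3 (15 min) + posttest (15 min) = 30 min = 0.5 h. That equals the cap per session, and only one session per day is allowed. The total load agrees: 4 assessments × 15 + 3 exercises × 15 = 105 min, which is the 1 hour 45 minutes in IV.6. For the comparison arm the total is 4 × 15 = 60 min, with 15 min on Day 5.

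**3. Which time points are affected?**

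| Assessment | Intervention arm | Comparison arm |
|---|---|---|
| Pretest, Day 1 | before Exercise 1 | alone |
| Posttest, Day 5 | after Exercise 3, same session | alone |
| Follow-up 1, Day 12 | alone | alone |
| Follow-up 2, Day 95 | alone | alone |

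Only the posttest has an exercise ahead of it in the same session.

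**4. Size of a possible bias.** The protocol gives no loss rates, so everything in this step is assumed: 50 per arm, 10% random loss in both arms, pretest–posttest correlation ρ = 0.5, pretest-adjusted analysis, no true effect. A further fraction q of the intervention arm is lost, and that loss correlates r with poorer response beyond what the pretest predicts.

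Bias in SD units = φ(z_q)/(1 − q) × r × √(1 − ρ²), with √(1 − 0.25) = 0.866.

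- q = 0.10: φ/(1 − q) = 0.1755/0.90 = 0.195.
- q = 0.20: φ/(1 − q) = 0.2800/0.80 = 0.350.

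| q | r | Bias (SD) | Share of d = 0.5 | Two-sided false-positive rate |
|---|---|---|---|---|
| 0 | – | 0 | 0 | about 5% |
| 0.10 | 0.3 | 0.195 × 0.3 × 0.866 = 0.051 | 10% | about 6% |
| 0.10 | 0.5 | 0.195 × 0.5 × 0.866 = 0.084 | 17% | about 7% |
| 0.20 | 0.3 | 0.350 × 0.3 × 0.866 = 0.091 | 18% | about 8% |
| 0.20 | 0.5 | 0.350 × 0.5 × 0.866 = 0.152 | 30% | about 12% |

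The design effect is d = 2f = 0.5. The false-positive rates come from simulation (8,000 runs per row). As a check on the last row: 50 × 0.9 × 0.8 = 36 against 50 × 0.9 = 45 clients gives SE = 0.866 × √(1/36 + 1/45) = 0.194. Then 0.152/0.194 = 0.78, and P(Z > 1.96 − 0.78) + P(Z < −1.96 − 0.78) is about 12%.

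**5. Cost in power.** This is small. If all 18 allowed losses fell in the intervention arm (32 against 50), the power formula in step 1, adapted to unequal arms, gives 78.8%, against 80.8% for 41 and 41. The issue is bias at posttest, not sample size.

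**The case against.** The strongest reply is that the protocol nowhere makes the posttest conditional on Exercise 3. It lists two items with their own times, and IV.6 is an ethics-form answer about burden, not a rule on survey routing. That stands. A reader might infer that missing outcomes depend on doing the exercises, or that outcomes are never requested from women who stop writing. The text supports neither: the schedule asks every client for all four assessments, and nothing cancels them.

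A reader might also infer that the withdrawal sentence in IV.5 makes leaving the study the only way to stop writing, so that the Day 12 and Day 95 data are lost too. That sentence assures clients that participation is voluntary. It does not equate stopping the exercises with withdrawal, and the follow-ups have no exercise attached.

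The magnitude can be challenged as well. Rates, correlations and direction are all assumed. Bundling itself can cost only women who would have answered a separate posttest; those who quit after Exercise 1 or 2 are a risk in any trial of this kind. In the 20% scenario, 5 comparison and 14 intervention clients are lost, 19 in all, slightly more than the 18 the plan allows for. The figures are therefore an illustration, not an estimate.

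Finally, the handling of missing data and the set of clients analysed may be in an analysis plan that is not shown. Those matters are left out of this point. What the reply does not remove is the schedule itself: one sitting, exercise first, in one arm.

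**Conclusion.** The point holds in a limited form. III.4 read with IV.6 places the posttest in the second half of a single 30-minute session in the intervention arm and alone in the comparison arm. That is an arm-specific hurdle before a named hypothesis time point, and it creates a risk of selective loss that over-enrolment does not address. It is a risk left open by the delivery, not a demonstrated loss.

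The size is unknown. Under the assumed scenarios it is about 0.05 to 0.15 SD at posttest, or 10% to 30% of the design effect, with a false-positive rate of about 6% to 12%. It is zero if loss does not differ between arms. The bundling does not reach the two follow-ups, and the sample size of 82 is unaffected. This is an inexpensive improvement to conduct, best made before data collection, and not an error in a stated figure.

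**What to change.** In III.4, state that the posttest is its own online link, sent on Day 5 to every randomised client in both arms with the same completion window, whether or not Exercise 3 was done. State also that clients who stop the exercises continue to receive the Day 12 and Day 95 questionnaires unless they decline them. The one-session-per-day entry in IV.6 should be worded to match; total time does not change.

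The cost is a separate survey link, a sentence or two, and one more email on Day 5. The estimated effect may be slightly diluted, because women who did not complete the exercises stay in the comparison. No further participants, visits or staff are needed.

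### Does a waitlist comparator without a writing task leave the question about body functionality unanswerable?

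*Protocol*

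**What the plan says.** The title (Protocol, II.1) asks: "Does focusing on body functionality improve body image among women who have undergone bariatric surgery". The background (III.1) states the aim in similar terms: "We would like to evaluate whether focusing on body functionality has a positive impact on the body image". The research questions (III.2) begin "Does focusing on body functionality lead to (1) a more" and go on to positive body image and positive self-image.

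The hypotheses, also in III.2, name the comparator. They open "In comparison to NOK clients in the waitlist comparison group" and predict improvement in the experimental group at posttest and at both follow-ups.

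Section III.4 sets out the arms. For the intervention: "Clients in the experimental group will complete all aspects of the study, described above". That means writing exercises on Days 1, 3 and 5 and four assessments. For the waitlist: "Clients in the comparison group will only complete the assessments at pretest, posttest, and follow-ups". Its access to the exercises comes later: "At the end of Follow-up 2, they can decide to receive the writing exercises".

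Section IV.10 asks "Are the subjects provided with all the information about the study beforehand" and the answer is yes. Section IV.11 says that no deception is used. Section III.7 records that the clinic wishes to use the intervention with its clients and has asked for its effectiveness to be evaluated.

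**The concern.** Read literally, the title and research question claim that the content of the exercises, attention to what the body can do, is the active ingredient. The two arms differ in more than content. The experimental group also does structured writing, spends extra time on the study and knows that it has received the programme. The outcomes are self-report questionnaires, clients are fully informed, and the participant-facing study name is Positive Body Image, so expectation is a credible rival explanation.

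If the trial were positive and reported in the words of its title, readers might take it as evidence for the functionality content, which a two-arm comparison with a waitlist cannot supply. The comparator is fixed by the design, so no analysis plan could separate these components afterwards.

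**Working it through.** **1. How far the arms differ.** Inputs are the schedule in III.4 and the participant load in IV.6.

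| Day | Experimental (min) | Waitlist (min) |
|---|---|---|
| 1 | 15 + 15 = 30 | 15 |
| 3 | 15 | 0 |
| 5 | 15 + 15 = 30 | 15 |
| 12 | 15 | 15 |
| 95 | 15 | 15 |
| Total | 105 | 60 |

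The 105 minutes agree with the 1 hour 45 minutes in IV.6. The difference is 105 − 60 = 45 = 3 × 15 minutes, which is the three exercises and nothing else. Day 3 is simply the second exercise in a study run wholly online, so it is not a separate difference. Eligibility (including for standard aftercare), the four assessments and the 15 Euro voucher are common to both arms.

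**2. Which contrast is tested.** The title, aim and research question refer to the functionality focus. The hypotheses refer to experimental group against waitlist, and III.4 randomises exactly that contrast, 50 to 50. The form field for III.2 asks for lay language, and III.1 describes the focus in earlier research as delivered through three structured writing exercises. In that context the phrase works as the everyday name of the programme. No passage claims to separate content from writing, attention or expectation.

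**3. The plan's sample size.** Inputs from III.5: f = 0.25, α = 0.05, power 80%, N = 82. From III.4: two groups and m = 4 measurements. Assumption, since the protocol does not state it: correlation ρ = 0.5 between measurements. For the between-groups effect in a repeated-measures analysis,

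λ = N·f²·m / [1 + (m − 1)ρ], with 1 and N − 2 degrees of freedom.

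- N = 82: λ = 82 × 0.0625 × 4 / 2.5 = 8.2, power 80.8%.
- N = 80: λ = 80 × 0.0625 × 4 / 2.5 = 8.0, power 79.8%.

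So 82 is reproduced for a two-group contrast. With 100 recruited, the dropout allowance is 1 − 82/100 = 18%. Nothing in the figure is wrong on this point.

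**4. What an active writing control would cost.** Same formula and ρ = 0.5. The effect sizes below 0.25 are assumptions, because the protocol gives no figure for a content-specific effect.

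| Assumed f | Total N for 80% power | Power with 82 completers |
|---|---|---|
| 0.25 | 82 | 81% |
| 0.20 | 126 | 62% |
| 0.15 | 220 | 40% |
| 0.10 | 494 | 20% |

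The planned size would still serve only if the content alone carried the full f = 0.25.

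**The case for a change.** The strongest case for acting is that the wording is wider than the contrast in three places (title, aim and research question), that correcting it costs nothing, and that the clinic intends to use the programme and may read a positive result as proof of the mechanism. The schedule adds to the worry: the third exercise and the posttest both fall on Day 5, so the experimental group may answer fresh from the exercise, with no counterpart in the waitlist arm. Nor does the protocol describe the comparator of the earlier experimental research, so it gives no independent ground for crediting the content.

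The factual part of this stands: the share of any effect due to content cannot be identified from two such arms. The call for a change does not follow. Rewording the lay question would leave every procedure and the tested hypothesis as they are, and the protocol contains no planned conclusion to correct. A neutral-writing arm would be a real change, but it would move the trial away from the clinic's question of whether offering the programme helps. It would also not secure the causal wording. With full prior information and no deception, clients given a neutral task would probably recognise it as such, and expectation would stay unequal.

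**Conclusion.** No change to the design, analysis or sample size is needed. Randomisation supports a causal conclusion about the three-exercise writing programme against waiting, among clients who qualify for standard aftercare. The hypotheses state that contrast, and it suits the clinic's request. The arms differ by 45 minutes of writing and by what comes with it, and the trial cannot divide an effect among those parts.

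The choice of a waitlist is a fair trade-off: it answers the practical question and forgoes the mechanistic one. This judgement rests on reading the lay research question alongside the hypotheses in the same section. The sample-size illustration further assumes ρ = 0.5 and the between-groups test. Authors may, if they wish, bring the title and lay question into line with the hypotheses. When results are written up, a benefit should be credited to the programme as a whole and not to its functionality content alone.
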